	
CelluTome™ system at TV1, TV5 and TV9, visits plus SOC (multi-layer compression) (Group 1A) (2) SOC alone (Group 2A).
 
At TV 7, wound assessment will be carried out to evaluate wound healing in Group 2A. Subjects in Group 2A, whose percentage area reduction (PAR) is <40% will be allowed to have CelluTome™ treatment in addition to continuation of SOC and will constitute Group 2C. Group 2C subjects will receive a graft at TV7 and TV11. The remainder of Group 2A subjects will be termed Group 2B subjects. Patient codes will still remain the same to enable tracking continuity.
 
During the Treatment Phase, the wound will be swabbed for protease activity for Group 1A and 2A/B subjects: TV1 (In Group 1A this will be prior to CelluTome™ application), TV5 and TV9 visits.
 
Subjects will be evaluated on a weekly basis during the Treatment Phase. Effectiveness evaluations each week will include Investigator assessment of wound healing and measurements of ulcer size using digital planimetry. At TV4 and TV8, Prisma™ is to be applied to the study ulcer for Group 1A, 2A, and 2B subjects. Group 2C subjects will receive Prisma™ at TV10. Safety evaluations during the Treatment Phase will consist of adverse event assessments at each visit.

Dosage and Frequency of Administration
	
Epidermal grafting will be applied up to three times in Group 1A: TV1, TV5 and TV9. Group 2C subjects will receive up to two grafts: TV7 and TV11.

Duration of Study
	
A run-in period of 2 weeks followed by 12 weeks of active treatment.

Statistical Methods, Power, and Sample Size Calculations
	
Please see the Statistical Analysis Plan in the protocol.

Protease Levels
	
Absolute values of inflammatory proteases (Neutrophil elastase, MMP 8 and 9) will be measured at S1 before application of Prisma™, day 0 before application of Epidermal grafts and week 4 and 8 visits thereafter to determine the effect of protease levels on graft success for Group 1A and 2A/B subjects. The results will be blinded to the Investigators.

Key Words
	
Epidermal Grafts Chronic Wounds Clinical Trial Venous Leg ulcer Protease levels in chronic wounds

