3 STUDY OUTCOMES

Primary outcome measure is time to heal in patients treated with epidermal grafting and SOC vs. SOC alone (**Group 1A** versus **Group 2A** at 6 weeks; and **Group 1A** versus **Group 2B** at 12 weeks).

Secondary outcomes include:

1. Percentage of wounds closed at 6 and 12 weeks.
2. Correlation between protease activity and healing at 4 and 8 weeks.
3. Incidence of adverse events at 12 weeks.
4. Pain reduction between baseline and 12 weeks.
5. Cost-effectiveness (see Appendix 19.4)
6. Cost-benefit (see Appendix 19.4)

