TREATMENT PHASE VISIT TV5 AND TV9

The following procedures must be performed:

- Pain assessment
- Assess compression bandaging
- Assess concomitant medications
- Check for any changes in the subject's health and update the Adverse Events or Serious Adverse Events pages with any events
- Study ulcer closure assessment will be determined by a blinded observer
 - If the study ulcer is 100% re-epithelialized, the subject will be scheduled for a Pre-Healing Confirmation Visit (HCV) one week later
 - If the study ulcer is healed, no other study procedures need to be completed at this visit
- Check for signs of clinical infection. If clinical diagnosis of infection has been made, then the subject can be treated with topical antimicrobials or oral antibiotics, but topical antibiotics CANNOT be used on the study ulcer. During the time that an infection is being treated, treatment with the IP will be stopped.
- Digital photo of the study ulcer
- Perform swab on study ulcer
- If in the epidermal grafting arm: Harvest epidermal grafts using the CelluTome™ device and then apply the grafts to the wound bed. (Procedure detailed in Appendix 10).
- If randomized to standard of care apply the provided foam to the wound.
- Apply multi-layer compression bandaging therapy
- Complete Quality of Life, PBI-P, and Time trade off questionnaires (see Appendices 19.5, 19.6, and 19.2)
- The next visit will be scheduled for one week

TREATMENT PHASE VISIT TV7

The following procedures must be performed:

- Pain assessment
- Assess compression bandaging

CELLUTOME™ IN VENOUS LEG

- Assess concomitant medications
- Check for any changes in the subject's health and update the Adverse Events or Serious Adverse Events pages with any events
- Study ulcer closure assessment will be determined by a blinded observer
 - If the study ulcer is 100% re-epithelialized, the subject will be scheduled for a Pre-Healing Confirmation Visit (HCV) one week later
 - If the study ulcer is healed, no other study procedures need to be completed at this visit
- Check for signs of clinical infection. If clinical diagnosis of infection has been made, then the subject can be treated with topical antimicrobials or oral antibiotics, but topical antibiotics CANNOT be used on the study ulcer. During the time that an infection is being treated, treatment with the IP will be stopped.
- Digital photo of the study ulcer

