6.4 SUBJECT COMPLETION AND WITHDRAWAL

SUBJECT COMPLETION

- A subject whose study ulcer has closed will be considered as having completed the study.
- A subject who completes the Treatment Phase will be considered as having completed the study.

SUBJECT PREMATURE WITHDRAWAL FROM THE STUDY

A subject who is randomized into the Treatment Period of the study but who does not complete the study through TV4 has prematurely discontinued.

All subjects have the right to withdraw at any point during treatment without prejudice. It will be documented whether or not each subject completed the clinical study. If for any subject, study treatment or observations were discontinued, the reason(s) will be recorded.

The Investigator can discontinue a subject at any time if it is considered medically necessary.

In addition, subjects WILL be withdrawn from the study, in consultation with the Medical Monitor and the Investigator, if any of the following are met:

- A subject is significantly non-compliant with the requirements of the protocol.
- A subject becomes pregnant (Note: the pregnancy will be followed up to term for safety follow-up. Relevant safety information collected after the study has completed will be reported as supplemental information.)
- A subject has revascularization surgery on the leg with the study (target) ulcer.
- A subject has a target ulcer wound bed that has exposed bone, tendon or fascia.
- The subject's study ulcer cannot be dressed with multi-layer compression.
- Two separate infections with no response to allowable treatments
- The subject's ulcer merges with an adjacent ulcer.

Premature withdrawal from the study MAY occur if:

- A subject is treated with a prohibited medication. This decision will be made by the Medical Monitor in conjunction with the Investigator as to whether premature withdrawal is warranted.

Every attempt should be made to collect follow-up information. The reason for treatment discontinuation or withdrawal from the study will be recorded in the source documents and on the appropriate page of the CRF.

Before a subject is identified as lost-to-follow up, the site should make all reasonable efforts to contact the subject. These attempts must be documented and should include at a minimum one phone call and one certified letter.

In the event that a subject is prematurely discontinued from the study at any time due to an adverse event of SAE, SAE procedures must be followed.

SCREEN FAILURES

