9.1.1 GENERAL

Descriptive statistical methods will be used to summarize the data from this study with hypothesis testing performed for primary and secondary endpoints. These include number of subjects (n), mean, median, standard deviation, minimum, and maximum for continuous data, and frequencies and percentages for categorical data. All data collected during the study will be reported and analyzed.

Unless specified otherwise, all statistical testing will be two-sided and performed using a significance (alpha) level of 0.05.

All statistical analyses will be conducted using PASW 19.

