The PP population for the 12-week study will comprise all subjects for which no protocol violations occurred and in which for both groups' complete data are available for all primary and secondary endpoints, and all covariates needed to conduct adjusted analyses.

SAFETY POPULATION

The safety population will be all subjects who have received at least CelluTome™ treatment or have completed the first visit (randomization, TV1).

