9.7 STATISTICAL METHODS

MISSING DATA

Missing data may be the result of missed visits, subjects lost to follow-up or who have died, or data not available (e.g., smoking status).

Missing primary endpoint data within 12 weeks from start of study will not be imputed for ITT populations as these will constitute right-censored data in the time to heal analysis. The last visit for which data are available will constitute the start of censoring (healing outcome). For secondary endpoints within 12 weeks from start of study, the last observation carried forward (LOCF) principle will be used for ITT populations.

For adjusted analyses of primary and secondary endpoints, missing data for covariates used to adjust analyses may be imputed in separate models when the missing data for each covariate is $\leq 30\%$ and it can be reasonably demonstrated that the missing data for each covariate are MCAR.

FINAL ANALYSIS

Analysis can be started when database lock for the trial is initiated. In regard to statistical modeling, the initial list of independent variables will be examined for correlation between pairs. In the event that

correlation (however calculated) exceeds 0.7, a selection will be made between the 2 variables to avoid possible issues of co linearity and variance inflation.

The following analysis will be conducted:

1. Flow chart (subjects)
2. Overall trial statistics (enrollment dates, site numbers, numbers of subjects)
3. Demographics between groups at baseline (no statistical testing but identification of likely trial imbalances)
4. Count of subjects in each group
5. Primary endpoints within 6 and 12 weeks (time to heal; previously defined by groups) will be analyzed by Kaplan-Meier and log rank test (unadjusted); and then Cox regression to adjust for the following variables (with and without covariate imputation):

- Site
- Year enrolled (if trial lasts 2 years or more)
- Treatment group
- Initial area at randomization (cm²)
- Initial wound depth (cm)
- Age of wound at enrollment (days)
- Smoking status
- Prior VLU
- Pain score at randomization
- Patient age
- Gender
- Ethnicity/race
- VCS score
- Diabetes
- Patient on pain medications
- Smoking status
- BMI
- Infection episodes

6. Secondary endpoints will be analyzed as follows:

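### The per-protocol rule requires complete data on every endpoint, so as written it excludes subjects whose ulcers close before the week-8 swab

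*Combined protocol and SAP*

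**What the plan says.** Section 9.6 (Patient Populations) names ITT, per-protocol and safety sets for the final analysis. Per-protocol membership needs the absence of protocol violations and also that "complete data are available for all primary and secondary endpoints, and all covariates needed to conduct adjusted analyses".

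The secondary endpoints in Section 3 include "Correlation between protease activity and healing at 4 and 8 weeks" and "Pain reduction between baseline and 12 weeks". Section 9.7 computes the protease change for each subject from baseline and the week-4 or week-8 value. The Synopsis says that "the wound will be swabbed for protease activity for Group 1A and 2A/B subjects", at TV1, TV5 (week 4) and TV9 (week 8).

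On closure, Section 6.4 says: "A subject whose study ulcer has closed will be considered as having completed the study". The TV5 and TV9 lists in Section 6.3 put the closure assessment before the swab and add: "If the study ulcer is healed, no other study procedures need to be completed at this visit".

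On missing secondary endpoint data, Section 9.7 says that "the last observation carried forward (LOCF) principle will be used for ITT populations". It gives no such rule for the per-protocol set, and its optional imputation concerns covariates only.

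**The concern.** A subject whose ulcer has closed by TV9 has no wound bed to swab under Appendix 19.7, so the week-8 protease value cannot exist. Nothing in the plan says that closure counts as complete data. That subject fails the per-protocol rule, and the reason is that the primary endpoint was reached. Membership of the set then depends on the outcome it is meant to analyse.

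A per-protocol set is normally read beside the ITT result as a check on it. A set from which the early healers have been taken out cannot do that for healed proportions, and it keeps only a fraction of the events.

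**Working it through.** **Inputs.** Section 9.3 gives 113 control and 112 graft subjects, control healing of 0.5 over 12 weeks, a hazard ratio of 1.74, weekly dropout of 0.033 (control) and 0.0083 (graft), and power of 86.1%. Section 9.1.1 says that "all statistical testing will be two-sided and performed using a significance (alpha) level of 0.05". Exponential healing is my assumption.

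**Reproducing the plan's power.**
- Healing hazards per week: ln 2 / 12 = 0.0578 (control) and 1.74 × 0.0578 = 0.1005 (graft).
- Dropout hazards: −ln(1 − 0.033) = 0.0336 and −ln(1 − 0.0083) = 0.0083.
- Expected events per arm: n × λ/(λ + δ) × [1 − exp(−12(λ + δ))], where λ is the healing and δ the dropout hazard. This gives 47.6 control and 75.4 graft, 123.0 in all.
- Schoenfeld power: Φ(√(123.0 × 0.25) × ln 1.74 − 1.96) = 86.7%. Freedman's formula gives 85.0%, and a Lakatos-type calculation 85.7% to 86.0%.

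All are within 2 points of 86.1%, so the healing model is a fair reading of the plan.

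**Share already closed at each visit that supplies a secondary endpoint**, before dropout: 1 − 0.5^(t/12) for Group 2A and 1 − 0.5^(1.74t/12) for Group 1A.

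| Closed by | Value lost | Group 2A | Group 1A |
|---|---|---|---|
| Week 4 | TV5 swab | 20.6% (about 23) | 33.1% (about 37) |
| Week 8 | TV9 swab | 37.0% (about 42) | 55.2% (about 62) |
| Week 11 | TV13 pain, if not collected after closure | 47.0% (about 53) | 66.9% (about 75) |

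With the 45% control healing quoted in Section 2.3, the week-8 shares are 32.9% and 50.0%.

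**What is left after the week-8 swab rule.**
- Retained: 113 × 0.630 = 71 and 112 × 0.448 = 50.
- Healing by week 12 among them: 1 − 0.5^(4/12) = 20.6% and 1 − 0.5^(1.74 × 4/12) = 33.1%, instead of 50% and 70.1%.
- Events: 71.2 × 0.206 + 50.1 × 0.331 = 31.3. Power by the same Schoenfeld formula, with allocation 71.2/121.3: 33%.
- Everyone retained was unhealed at week 8, so, recurrence aside, the 6-week primary comparison would have no events in this set.

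If a week-12 pain score is also required and is not collected after closure, about 60 and 37 subjects remain, with about 7 events and 10% power. If closure counted as complete data, nobody would be lost for healing: 113 × 0.5 + 112 × 0.701 = 135 events and about 90% power before dropout.

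**Against Group 2B, the 12-week comparator.** Section 5.1 expects 30% of Group 2A to switch to Group 2C. If no switcher has healed by week 8 (assumption), the Group 2B loss is 0.370/0.70 = 52.9%, against 55.2% in Group 1A. With 10% to 40% switching, the Group 2B figure runs from 41% to 62%.

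**Group 2C.** The Synopsis and Section 4 limit treatment-phase swabs to Groups 1A and 2A/B. The TV9 list in Section 6.3 does not repeat that limit. If Group 2C is not swabbed, its subjects also fail a literal reading: 0.30 × 113 = about 34. Added to the 42 early healers, that is 76 of 113 (67%) of the control arm, on the same assumption.

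**The case against.** The best defence is that the sponsor did not mean this. Section 6.4 calls a subject with a closed ulcer a completer, and Section 9.7 does not list closure among the causes of missing data. Post-closure values might therefore be regarded as not applicable rather than missing. That is a sensible intention, but the plan does not state it, and the rule as written asks for complete data on all endpoints.

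The consequence is also limited. Section 9.7 assigns no listed test to the per-protocol set, and the rule does not touch the ITT analysis. Both points stand. The set is nevertheless declared for the final analysis.

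Three stronger readings are tempting, and the documents do not support them:

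- **That the rule necessarily removes more graft subjects.** For 1A vs 2A this holds only if the graft works; with no effect, the loss is 37.0% in both arms. Against Group 2B the direction is not assured. If unswabbed Group 2C subjects are counted, the control arm may lose more.
- **That the per-protocol hazard ratio is biased.** Under the constant hazards used here it stays 1.74 after week 8. The calculation shows no distortion of the hazard ratio.
- **That no healed subject can have a week-12 pain score, so 50% and 70% are lost.** The waiver in Section 6.3 covers procedures at that visit and does not forbid later data. A confirmation visit follows closure, and Section 9.7 lists recurrence by 12 weeks and pain at TV13. The TV13 list also contains pain without a healed exemption, so a subject first found closed there has a score. The upper figures are 47% and 67%, and they apply only if pain is not collected after closure.

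**Conclusion.** The concern holds: as written, the per-protocol rule selects on the primary outcome. The week-8 swab is enough to show it, because no effort by a site can produce a wound swab from a closed ulcer.

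The losses of about 37% of Group 2A and 55% of Group 1A rest on exponential healing, 50% control healing and a hazard ratio of 1.74, before dropout. The harm is to healed proportions, event count and power. Selection on outcome remains even if the arms lose equal shares. This should be corrected before the per-protocol set is used, but it does not threaten the ITT conclusion.

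**What to change.** In the per-protocol paragraph of Section 9.6, delete the condition that complete data be available for all primary and secondary endpoints. Keep the protocol-violation criterion as it stands; this point gives no reason to alter it. Then state that each endpoint is analysed in the per-protocol subjects for whom it is defined, and that values not obtainable after closure do not exclude a subject. The same sentence settles Group 2C for the protease endpoints.

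The cost is SAP wording only, with no new data, visits or sample size. The number analysed will differ by endpoint, so each table should report it.

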9.7 STATISTICAL METHODS

MISSING DATA

Missing data may be the result of missed visits, subjects lost to follow-up or who have died, or data not available (e.g., smoking status).

Missing primary endpoint data within 12 weeks from start of study will not be imputed for ITT populations as these will constitute right-censored data in the time to heal analysis. The last visit for which data are available will constitute the start of censoring (healing outcome). For secondary endpoints within 12 weeks from start of study, the last observation carried forward (LOCF) principle will be used for ITT populations.

For adjusted analyses of primary and secondary endpoints, missing data for covariates used to adjust analyses may be imputed in separate models when the missing data for each covariate is $\leq 30\%$ and it can be reasonably demonstrated that the missing data for each covariate are MCAR.

FINAL ANALYSIS

Analysis can be started when database lock for the trial is initiated. In regard to statistical modeling, the initial list of independent variables will be examined for correlation between pairs. In the event that

correlation (however calculated) exceeds 0.7, a selection will be made between the 2 variables to avoid possible issues of co linearity and variance inflation.

The following analysis will be conducted:

1. Flow chart (subjects)
2. Overall trial statistics (enrollment dates, site numbers, numbers of subjects)
3. Demographics between groups at baseline (no statistical testing but identification of likely trial imbalances)
4. Count of subjects in each group
5. Primary endpoints within 6 and 12 weeks (time to heal; previously defined by groups) will be analyzed by Kaplan-Meier and log rank test (unadjusted); and then Cox regression to adjust for the following variables (with and without covariate imputation):

- Site
- Year enrolled (if trial lasts 2 years or more)
- Treatment group
- Initial area at randomization (cm²)
- Initial wound depth (cm)
- Age of wound at enrollment (days)
- Smoking status
- Prior VLU
- Pain score at randomization
- Patient age
- Gender
- Ethnicity/race
- VCS score
- Diabetes
- Patient on pain medications
- Smoking status
- BMI
- Infection episodes

6. Secondary endpoints will be analyzed as follows:

- Proportion of wounds healed at 12 weeks will be analyzed by chi square (unadjusted); this endpoint may also be analyzed using logistic regression to adjust for the following variables (with and without covariate imputation) if needed:
 - Site
 - Year enrolled (if trial lasts 2 years or more)
 - Treatment group
 - Initial area at randomization (cm²)
 - Initial wound depth (cm)
 - Age of wound at enrollment (days)
 - Smoking status
 - Prior VLU
 - Pain score at randomization

- Patient age
- Gender
- Ethnicity/race
- VCS score
- Diabetes
- Patient on pain medications
- Smoking status
- BMI
- Infection episodes

Note: unadjusted testing for **Group 2C** versus **2B** will be non-inferiority, followed by superiority testing if the former fails and proportion of wounds healed in **Group 2C** is much higher than in **Group 2B**.

- A summary of the incidence of adverse events (count by patient):
 - AE (category)
 - SAE (category; brief description; resolution; should include death)
 - When event happened in relation to start of treatment (days)
 - Associated patient ID, site ID

Incidence of AEs will be analyzed by Mann-Whitney test on a per subject basis.

- Correlation of changes in wound area with changes in protease activity will be first analyzed by calculating the Pearson correlation coefficient for each group or Spearman's rho if data are grossly non-normal. For each subject the change in protease activity is calculated by subtraction of the value at 4 or 8 weeks from the value at baseline; reduction in wound area is calculated similarly. Differences in r will be analyzed using Steiger's Z test with the assumption that r will have the same sign for both groups. If significant differences are found between groups, further analysis using GLM doubly multivariate repeated measures (change in wound area and protease activity between baseline and 4 and 8 weeks) to adjust for the following variables (with and without covariate imputation) may be undertaken (ordinal re-categorization will be done if data are severely non-normal):
 - Site
 - Year enrolled (if trial lasts 2 years or more)
 - Treatment group
 - Initial area at randomization (cm²)
 - Initial wound depth (cm)
 - Age of wound at enrollment (days)
 - Smoking status
 - Prior VLU
 - Pain score at randomization
 - Patient age
 - Gender
 - Ethnicity/race
 - VCS score

CELLUTOME™ IN VENOUS LEG

- Diabetes
 - Patient on pain medications
 - Smoking status
 - BMI
 - Infection episodes
- Reduction in pain score (baseline – Week 12) will be analyzed by paired t test if the dependent variable data are not grossly non-normal or the Mann-Whitney test if they are grossly non-normal (unadjusted).

To create the flow chart, the following numbers will be required for each group: eligible (n), screened (n), screen failure (n, with categorical reasons), randomized (n), completed 12 weeks study (n), withdrawals or lost to follow-up after randomization (n, with categorical reasons).

These variables are required for the final analysis:

- Site ID (alphanumeric)
- Patient ID (alphanumeric)
- Year enrolled (numeric; date, year only)
- Group assignment (nominal factor, [1A, 2A, 2B, 2C]; note: subjects in 2A can also have 2B or 2C assignments as well)
- Lost to follow up (binomial factor [1,0; 1 = yes]; estimated date lost to follow-up; associated patient ID; categorical reason for lost to follow-up)
- Death during study (binomial factor [1,0; 1 = yes]; estimated date when death occurred)
- Gender (nominal factor [1, 0; male = 1])
- Subject age at S1 (continuous variable with breakpoint at > 90 years if > 90)
- Ethnicity/race (multinomial factor)
- Smoking status at S1 (ordinal factor: [1, 2, 3; never, ever, current])
- Wound count (Poisson distribution variable; count of VLU at patient level at randomization)
- Index Ulcer location (multinomial factor)
- Prior VLU at S1 (binomial factor [1,0; 1 = yes])
- Wound age at S1 (continuous variable, days; S1)
- Pain score (continuous variable, 0-10, TV1 and 13)
- VCS score at S1 (continuous variable, 0-24)
- BMI at S1 (continuous variable)
- Diabetes at S1 (nominal factor [1, 0; yes = 1])
- Subject on pain medication at S1 (nominal factor [1, 0; yes = 1])
- Wound area (continuous variable, cm²; weekly, weeks TV1-13)
- Wound depth (continuous variable, cm; weekly, weeks TV1-13)
- Outcome healed at 12 weeks (binomial factor, [1,0; 1 = yes])
- Time to heal (continuous variable, 0-84, days after randomization for healed wounds)
- Initial wound healed within 12 weeks and confirmed closed about 2 weeks later (binomial, [1,0; 1 = yes])
- Ulcer recurrence by 12 weeks (binomial factor, [1,0; 1 = yes]; estimated days after randomization when event occurred)
- Infection episode (Poisson variable, weeks TV1-13)
- AE (Poisson distribution variable, count at patient level; date of onset)

CELLUTOME™ IN VENOUS LEG

- TEAE (Poisson distribution variable, count at patient level for each of 4 categories; date of onset)
- SAE (Poisson distribution variable, count at patient level; date of onset; resolution; brief description)

ADJUSTMENT FOR FEWR

Adjustment to control for the family wise error rate (FEWR) (also known as multiplicity of testing) will use the Hochberg step-up procedure thus: Let $p_1 \geq p_2 \geq \dots \geq p_K$ be the ordered p-values and H_1, H_2, \dots, H_K be the corresponding null hypotheses. Reject H_k and all H_j for $j \leq k$ if $p_k \leq \alpha/k$. The adjusted p-values are $p_{adj,k} = \min \{p_1, 2p_2, \dots, kp_k\}$ for $k = 1, 2, \dots, K$.

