8.6 PAIN ASSESSMENTS

Pain intensity of the VLU is to be assessed before any dressing changes or other wound manipulations at all screening visits, treatment visits, and at follow-up period visits.

Subject will be asked to rate his/her pain on a scale of 0 to 10 with 0 being “no pain” and 10 being the “worst pain possible”.

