from the mean change in wound area and protease activity between baseline and 4 weeks after 4 weeks of CelluTome™ + SOC (**Group 1A**) versus 4 weeks of SOC (**Group 2A**) will be equal for both groups. Formally, $H_0: r_1 - r_2 = 0$; $H_1: r_1 - r_2 = D_1 \neq 0$, where r_1 is the Pearson correlation coefficient for subjects in **Group 1A** calculated from difference in mean wound area and difference in mean protease activity between baseline and 4 weeks, r_2 is the same specified metric for subjects **Group 2A**, D_1 is the difference ($r_1 - r_2$) assuming the alternative hypothesis, and the statistical test used is Steiger's Z test with the assumption that r will have the same sign for both groups.

H5: Correlation of wound area with protease activity at 8 weeks

The Pearson correlation coefficient (or Spearman's rho in the case of severe non-normality) calculated from the mean change in wound area and protease activity between baseline and 8 weeks after 8 weeks of CelluTome™ + SOC (**Group 1A**) versus 8 weeks of SOC (**Group 2B**) will be equal for both groups. Formally, $H_0: r_1 - r_2 = 0$; $H_1: r_1 - r_2 = D_1 \neq 0$, where r_1 is the Pearson correlation coefficient for subjects in **Group 1A** calculated from difference in mean wound area and difference in mean protease activity between baseline and 8 weeks, r_2 is the same specified metric for subjects in **Group 2B**, D_1 is the difference ($r_1 - r_2$) assuming the alternative hypothesis, and the statistical test used is Steiger's Z test with the assumption that r will have the same sign for both groups.

H6: Reduction in pain score at 12 weeks

The change in mean pain score between baseline and at 12 weeks after 12 weeks of CelluTome™ + SOC (**Group 1A**) versus 12 weeks of SOC (**Group 2B**) will be equal for both groups. Formally, $H_0: \mu_1 - \mu_2 = 0$; $H_1: \mu_1 - \mu_2 = D_1 \neq 0$, where μ_1 is the mean difference in pain score for subjects in **Group 1A** between baseline and 12 weeks, μ_2 is the same specified metric in **Group 2B**, D_1 is the difference ($\mu_1 - \mu_2$) assuming the alternative hypothesis, and the statistical test used is the paired t test if data are normal and the Mann-Whitney test on a non-paired basis if data are non-normal.

H7: Proportion of wounds healed at 12 weeks (Groups 2B versus 2C)

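### Carrying the last value forward mishandles subjects who leave because they healed: it distorts the H4 and part of the H5 protease correlations and leaves week-12 pain (H6) ambiguous

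*Combined protocol and SAP*

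**What the plan says.** - **Missing-data rule (SAP 9.7).** For secondary endpoints up to week 12, "the last observation carried forward (LOCF) principle will be used for ITT populations". No secondary endpoint is excepted. The causes named are these: "Missing data may be the result of missed visits, subjects lost to follow-up or who have died, or data not available". Exit because the ulcer healed is not among them.
- **Exit at closure (6.4).** "A subject whose study ulcer has closed will be considered as having completed the study".
- **Healed visits (6.3, including TV5 and TV9).** "If the study ulcer is healed, no other study procedures need to be completed at this visit". On the TV5 and TV9 lists the swab comes after this instruction, so an ulcer found healed there need not be swabbed.
- **Swabs (synopsis, Protease Levels).** Proteases "will be measured at S1 before application of Prisma™, day 0 before application of Epidermal grafts and week 4 and 8 visits thereafter".
- **H4 and H5 (9.2).** The correlation in each group is "calculated from the mean change in wound area and protease activity" between baseline and week 4 or week 8. Neither 9.2 nor 9.7 says whether baseline is S1 or TV1.
- **Pain.** Under 8.6, "Pain intensity of the VLU is to be assessed before any dressing changes or other wound manipulations at all screening visits, treatment visits". The list of variables for the final analysis in 9.7 keeps pain at TV1 and TV13 only.
- **Comparators (9.2).** H4 compares Group 1A with 2A. H5 and H6 compare 1A with 2B.

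**The concern.** Most missing secondary data in this trial would come from success, not from loss to follow-up. A healed ulcer yields no swab, and a subject who closed before TV13 normally has no TV13 pain score. A rule written for missed visits and losses would therefore act mainly on healers.

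For H4, a subject healed by TV5 has TV1 as the last swab. Carried forward and subtracted from a TV1 baseline, it gives a change of zero beside the largest possible area reduction for that ulcer. These points are artefacts, they sit at one extreme of the area axis, and more of them fall in the arm that heals faster. A difference in correlation between arms could then reflect healing rates and not protease biology.

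For H6, the value carried forward depends on which pain scores are in the dataset, and the plan points both ways. On one reading, the subjects who did best are recorded as having no pain relief.

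**Working it through.** **1. Reproduce the plan's figure.** Inputs from 9.3: 113 control and 112 treatment subjects, control healing 0.5 at 12 weeks, hazard ratio 1.74, weekly dropout 0.033 and 0.0083, two-sided alpha 0.05. With exponential healing (control hazard ln 2/12 per week, treatment 1.74 times that), a Lakatos-type logrank calculation gives 123 expected events and power of 85.7% (fine grid) to 86.0% (weekly grid). The plan states 86.1%, so these healing curves represent its assumptions.

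**2. Healed share by week t, before dropout.** Control: 1 − 0.5^(t/12). Group 1A: 1 − 0.5^(1.74t/12).

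| Healed by | Control (all 2A) | Group 1A |
|---|---|---|
| Week 4 (TV5) | 20.6%, about 23 of 113 | 33.1%, about 37 of 112 |
| Week 8 (TV9) | 37.0% | 55.2% |
| Week 11 (TV12) | 47.0%, about 53 | 66.9%, about 75 |

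With 10% dropout per arm (5.1; exponential timing assumed), the week-4 shares are 20.3% and 32.6%, and the week-11 shares 45.1% and 64.3%. Healing then accounts for about 87% of control exits and 92% of 1A exits.

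**3. H4 (week 4, 1A versus 2A).** The 20.6% and 33.1% healed by TV5 have a carried-forward change of TV1 − TV1 = 0 if baseline is TV1. If baseline is S1, the change is S1 − TV1. That is a real difference, but it comes from the run-in and not from the treatment period.

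**4. H5 (week 8, 1A versus 2B).** Those healed after TV5 and by TV9 number 37.0 − 20.6 = 16.4% of control and 55.2 − 33.1 = 22.1% of 1A. They carry a real week-4 swab. Zero change therefore applies to 20.6/37.0 = 56% (control) and 33.1/55.2 = 60% (1A) of those healed by week 8. Section 5.1 expects 30% of 2A to move to 2C, and these are unhealed at week 6. The zero-change share of 2B is then 20.6/70 = 29%, against 33% of 1A.

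**5. Effect on the correlation (illustration only).** The documents give no protease mean or SD, so standard-normal scales are assumed. The true correlation is 0.5 in both arms. The top 20.6% (control) and 33.1% (1A) on area reduction are treated as healed and given zero protease change.

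| Assumed mean protease fall | LOCF, control / 1A | Swabbed only, control / 1A |
|---|---|---|
| 0 SD | 0.33 / 0.33 | 0.40 / 0.37 |
| 0.5 SD | 0.16 / 0.10 | 0.40 / 0.37 |
| 1 SD | 0.00 / −0.13 | 0.40 / 0.37 |

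LOCF pulls both correlations down. Once protease falls on average, it also separates the arms, and at 1 SD it reverses the sign in 1A, although the plan's test assumes the same sign in both groups. Swabbed-only values are also below 0.5, because the healed end of the range is removed.

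**6. H6 (week 12, 1A versus 2B).** Pain is on the TV13 list, so an ulcer first closed at TV13 still has a score, and week 11 is the relevant cutoff. No TV13 score is expected for 66.9% of 1A and 47.0% of all control. For 2B, with 30% moved to 2C:
- Upper bound, all counted healers in 2B: 47.0/70 = 67%.
- Lower illustration, 2C subjects healing after week 6 at the same rate as other open control ulcers: 29.3% of control heal by week 6, all in 2B. The later 17.7% split in proportion to open ulcers: 17.7 × 40.7/70.7 = 10.2. Then (29.3 + 10.2)/70 = 56%.

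If weekly scores are used, the carried value is from about the closure visit. If only TV1 and TV13 are held, it is TV1, and the reduction is TV1 − TV1 = 0.

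**The case against.** **LOCF may not be meant for healers.** Section 9.7 names other causes of missing data, and 6.4 counts closed ulcers as completed. That is a fair reading of intent. But the LOCF sentence has no exception and no other rule covers values after closure, so the plan either imputes as described or says nothing for a large share of subjects. Both need correcting.

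**Stronger readings that the documents do not support.**
- A reader might infer that every healed subject gets zero protease change. Exact zero needs healing by TV5 and a TV1 baseline.
- A reader might infer that LOCF invents week-12 pain. Pain is listed first at each treatment visit in 6.3, so a healer normally has a real score from about closure. The artificial zero arises only if the TV1/TV13 list is taken literally.
- A reader might infer a large imbalance between arms throughout. It is clear for H4 (21% versus 33%). Against Group 2B it is small for the zero-change points in H5 (29% versus 33%), and it may nearly vanish for missing pain (56% to 67% versus 67%).
- A reader might extend the criticism to H2. Carrying healed status forward is reasonable there, apart from recurrence.

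**Restricting to swabbed subjects has its own bias.** This stands. It selects on a post-randomisation outcome and leaves the healers out of an endpoint about healing. It avoids artificial data points but answers a narrower question, and the report must say so.

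**The per-protocol set is no safeguard.** It requires complete data on all endpoints (9.6), so read literally it would drop most healers.

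**Conclusion.** The concern holds for H4, for part of H5, and as an unresolved rule for H6. Under the 9.3 healing assumptions, and with TV1 as baseline, LOCF would enter an artificial zero protease change beside complete area loss for about 21% of control and 33% of Group 1A at week 4. About 67% of 1A, 47% of all control and up to about 67% of Group 2B would have no TV13 pain score. The 2B figure assumes that 30% move to 2C and that all counted healers stay in 2B.

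These are counts of subjects exposed to the rule. Bias in pain or protease units cannot be computed, because the documents give no means or SDs. The primary time-to-heal analysis uses censoring, so it and the 86.1% power are untouched. The change should be made before analysis, but it does not threaten the main conclusion.

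**What to change.** In SAP 9.7, name healing as a cause of missing data, then:

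- **H4 and H5.** Remove LOCF. Define baseline as S1 or TV1. Analyse only subjects swabbed at the visit concerned, report the number swabbed by arm, and state that the result applies to ulcers still open.
- **H6.** Add weekly pain to the variable list, which reconciles it with 8.6. Replace LOCF with a repeated-measures mixed model on all weekly scores, with baseline pain, visit, arm and arm-by-visit. The model assumes that observed scores account for who leaves, which healing may violate. So add a sensitivity analysis that holds healed subjects at their closure-visit score.
- **H2.** Healed status may still be carried forward, with recurrence dealt with explicitly.

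**Cost.** SAP wording and modest programming; weekly pain is already scheduled up to closure. H4 and H5 lose subjects: before dropout, about 23 of 113 control and 37 of 112 in 1A at week 4. Their selection on healing must be stated. None of this removes the separate selection in comparing 1A with Group 2B.
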